Our study plans to randomize treatment naive patients with vestibular migraine to an 8 week trial of an escalating dose of either nortriptyline or topiramate followed by an 8 week crossover to the other drug if patient is willing, if patient wants to stay on first medication we will just continue to follow. During the first 8 weeks if there is an intolerance to the first drug they can be switched to the other drug at any point and then followed on that medication for the remainder of the study. Response to therapy will be quantified by the Migraine Specific Quality of Life (MSQ) and Dizziness Handicap Inventory (DHI) administered at multiple time points during the study. Three groups of patients that will be eligible for the study will include 1)Patients with Neuhauser dVM; 2)Patients with pVM; and 3) Patients with dizziness that falls outside the Neuhauser criteria (non-Neuhauser vestibular migraine or nNVM).

Our hypothesis is that even patients with dizziness outside of the Neuhauser dVM and pVM spectrum will respond to treatment for vestibular migraine, and thus likely have migraine as a cause of their dizziness. Previous research by our group has suggested that such patients do in fact respond to migraine therapy1. A second goal of the study is to evaluate the comparative efficacy of nortriptyline and topiramate in the treatment of these three subgroups of patients with vestibular migraine.

Page numbers from a sponsor's protocol/grant may be referenced in 2b and 2c.

b) **List your research objectives (specific aims & hypotheses of the study).**

The primary goal of the study is to evaluate the comparative effectiveness of migraine diet, nortriptyline and topiramate in the treatment of these three subgroups of patients with vestibular migraine. A secondary hypothesis is that even patients with dizziness outside of the Neuhauser dVM and pVM spectrum will respond to treatment for vestibular migraine, and thus likely have migraine as a cause of their dizziness. Previous research by our group has suggested that such patients do in fact respond to migraine therapy ([name], 2012).

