opening the lowest numbered of a stack of envelopes which will contain a randomly preselected card indicating which drug is to be used. The nortriptyline will be given in an escalating fashion, starting at 25 mg PO qhs for 2 weeks, followed by 50 mg PO qhs for 2 weeks, and finally 75 mg PO qhs. Patients will be encouraged to use the lowest effective dose and to self-titrate their medication. Topiramate dosing will be 25 mg PO qhs for 1 week, followed by 25 mg BID for 1 week, followed by 25 mg in the morning and 50 mg qhs for 1 week, and finally 50 mg BID. Patients will be allowed considerable leeway in adjusting their dosage and will be encouraged to stay on the lowest effective dose. Medication will be provided open label to the patient and paid for through the patients' insurance, as this intervention falls within current standard practice, and is not investigational.

After two, three and four months on drug patients will be brought into the clinic for a office visit or contacted by phone with history, and will complete MSQ V2.1, DHI, C-SSRS and the MoSQ, then patients will be offered the opportunity to switch to the other drug. Those patients who wish to switch drugs will first be weaned off their current drug over a one week time period. Patients who elect to stay on their initial drug will be followed for a total of four months. Patients who opt for trial of a second drug will then be started on the second drug via a self-titrating protocol as described above and followed on that drug for up to 4 months.

Our clinical experience has shown that on occasion patients will refuse to take more than a few doses of nortriptyline or topiramate due to intolerable side effects. Such patients will be allowed to immediately initiate therapy with the other drug. The medication change can be done with a phone call to their pharmacy without an office visit, as is done in standard of care. Also, patients who already follow a rigorous migraine diet will be allowed to enter the drug treatment phase immediately. In our experience, such patient make up less than 5% of the population that presents for treatment of vestibular migraine.

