Our clinical experience has shown that on occasion patients will refuse to take more than a few doses of nortriptyline or topiramate due to intolerable side effects. Such patients will be allowed to immediately initiate therapy with the other drug. Otherwise the physician will be in close contact with the patients and if there are any concerns or problems patients will be given the option to stop or switch treatment methods and if the PI feels necessary will recommend alternative treatment.

d) Describe how data analysis will be performed (statistical tests, methods of evaluating data) and indicate the smallest group/unit for which separate reporting will occur. For studies involving a questionnaire, if data and reliability information are available, please describe or provide

Protocol Title: A Prospective randomized cross-over trial of nortriptyline and topiramate in the initial treatment of vestibular migraine

references. For full board, unfunded studies describe sample size determination and power analysis. If none, please justify.

The core of the analysis plan includes two components: (1) nortriptyline versus topiramate comparison at two-months and (2) cross-over. In addition to measuring differences in patient-reported effectiveness/acceptability between nortriptyline versus topiramate for the first component, repeated measures ANOVA will be employed to assess change in Migraine Specific Quality of Life (MSQ) and Dizziness Handicap Inventory (DHI) between the groups. A subgroup analysis for the three subtypes of vestibular migraine will be also conducted. Descriptive statistics for subject attributes will be reported by group and assessed for potential confounding. In the second component, data from subjects who choose to try the alternate medication will be used for the cross-over analysis. This plan calls for comparing change in each subject's DHI score for their experience using nortriptyline versus topiramate. With this approach each subject serves as its own control, which helps to minimize selection bias in this component of the study. Significance will be set at the alpha level of 0.05 for both components of the analysis plan. All analyses will be coordinated by [name] and staff at the Saint Louis University Center for Outcomes Research, an academic unit that specializes in statistical analysis for clinical studies.

Please save frequently

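### The cross-over analysis uses only patients who choose to switch drug; pairing each with themselves does not remove that selection or a period shift, so it should be supportive only

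*Combined protocol and SAP*

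**What the plan says.** Section 3d of the combined protocol and SAP sets out two core components: the randomised comparison at two months, and the cross-over. For the second, "data from subjects who choose to try the alternate medication will be used for the cross-over analysis". The measure is the change in each patient's "DHI score for their experience using nortriptyline versus topiramate". The stated rationale is: "With this approach each subject serves as its own control, which helps to minimize selection bias in this component of the study". On error level: "Significance will be set at the alpha level of 0.05 for both components of the analysis plan". No test, period term, sequence term or method for non-switchers is given for this component.

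Sections 2a and 3b describe how a patient comes to switch:

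- Treatment is known to the patient: "Medication will be provided open label to the patient".
- The choice follows the first-drug assessment. Patients attend or are phoned "and will complete MSQ V2.1, DHI, C-SSRS and the MoSQ, then patients will be offered the opportunity to switch to the other drug".
- Section 2a makes the cross-over depend on the patient's willingness. Those who prefer the first drug stay on it and are followed.
- There is a second, earlier route: "if there is an intolerance to the first drug they can be switched to the other drug at any point".
- Section 3b, near its end, says the investigators expect patients who benefit to remain on treatment.

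**The concern.** Entry to the cross-over set is decided after randomisation, by the patient, who knows the drug and has just experienced its effect. Two things follow that pairing cannot repair.

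First, patients who switch because their first-drug DHI was poor will tend to score better next time whatever they take. Within each sequence this looks like a benefit of the second drug. Whether it cancels between sequences depends on how many switch in each arm, and on how the two sequences are combined.

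Second, if scores drift between periods for any common reason, the drift cancels in a pooled paired difference only when the two sequences are of equal size. Voluntary switching gives no reason to expect that.

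What is at stake is how one of two core analyses is read. A significant cross-over result at 0.05 could partly reflect who switched and when, while the protocol tells the reader that the design guards against selection.

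**Working it through.** **Inputs from the documents.** Section 3b gives 45 patients per arm and assumed effectiveness/acceptability of 60% (nortriptyline) and 30% (topiramate).

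**The plan's own figure.** It concerns component 1 only. With a pooled Z-test, two-sided 0.05:
- standard error under no difference = √(2 × 0.45 × 0.55/45) = 0.1049
- standard error under the alternative = √((0.24 + 0.21)/45) = 0.100
- power = Φ((0.30 − 1.96 × 0.1049)/0.100) = Φ(0.944) = 82.8%

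This agrees with the stated 82%. No figure is given for component 2.

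**Assumptions, none in the documents.** DHI SD is 20, with a higher score worse. Within-patient correlation ρ is 0.4 to 0.8. A common period shift is 0 to 10 points of improvement. Patients who do not find the first drug acceptable switch, so 40% switch from nortriptyline and 70% from topiramate: 18 and 31.5 patients, 49.5 in all. Within each arm, those with the worst first-drug DHI switch. There is no true drug difference.

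**Step 1: apparent gain within a sequence.** If a fraction p of an arm switches, the expected improvement from first to second drug is (1 − ρ) × 20 × φ(z_p)/p.
- Here φ(z)/p = 0.3863/0.40 = 0.966 and 0.3477/0.70 = 0.497.
- Nortriptyline first: 11.6 points at ρ = 0.4, 3.9 at ρ = 0.8.
- Topiramate first: 6.0 points at ρ = 0.4, 2.0 at ρ = 0.8.

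These gains arise with no drug effect and survive pairing.

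**Step 2: pooled paired mean (nortriptyline minus topiramate).** The two gains enter with opposite signs, weighted by the number of switchers.
- Selection part = (1 − ρ) × 20 × (0.3863 − 0.3477)/1.1 = 0.42 points (ρ = 0.4) to 0.14 (ρ = 0.8), against nortriptyline. Simulated type I error from this part alone is about 5%.
- Period part = (31.5 − 18)/49.5 = 27% of any common shift. A 5-point improvement gives 0.27 × 5 ≈ 1.4 points, and a 10-point improvement gives about 2.7, in favour of nortriptyline.

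**Step 3: period-adjusted estimate in switchers only.** Averaging the two sequence means removes the period part. What remains is half the difference between the two gains: (11.6 − 6.0)/2 = 2.8 points at ρ = 0.4, and (3.9 − 2.0)/2 ≈ 0.9 at ρ = 0.8. Simulated type I error is about 8% (ρ = 0.8) to 16% (ρ = 0.4). The usual crossover remedy therefore exchanges one bias for the other.

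**Step 4: equal switching.** If p is the same in both arms and for the same reasons, the two gains are equal and the sequences are the same size. Both parts then vanish, whichever way the sequences are combined.

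**The case against.** The strongest reply is that the protocol says pairing helps to minimise selection bias, not that it removes it. Pairing does deal with stable differences between the kinds of patient who switch from each drug. That stands: the sentence is incomplete rather than false.

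The second reply is that selection on outcome nearly cancels in a simple pooled mean, so most of the computed bias there comes from an assumed period shift. That also stands for the pooled mean. It does not stand for a period-adjusted estimate, and the plan does not say which would be used. A reader might infer that section 3d prescribes a pooled paired test with a known error rate. It prescribes only a comparison of each patient's DHI change, so the error rates above belong to candidate analyses, not to the plan.

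Third, 40% and 70% switching with no true DHI difference needs some other cause, such as tolerability, because one DHI cut-off in both arms would then give equal switching. This is fair. If a true difference produces those rates through a common cut-off, it would be about 20 × (0.524 + 0.253) ≈ 16 points. The bias arithmetic in steps 1 to 3 is unchanged, although type I error no longer applies. With a smaller true difference of 5 points, switching would be about 47–50% and 60–63%. Bias in the pooled mean is then only +0.2 to −1.3 points, with no excess of intervals missing the truth.

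Finally, the expectation that patients who benefit will stay is written about continuing or tapering treatment, not about the two-month offer. It still shows the behaviour that the investigators anticipate, and section 2a makes switching a matter of preference.

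**Conclusion.** The point holds in a limited form. Component 2 is selected after randomisation. Pairing does not correct for that or for a period shift with unequal sequences, and nothing visible in the plan does.

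The size cannot be fixed from the documents. Under the assumptions above it is 0.1 to 0.4 points from selection plus 27% of any period shift for a pooled mean, or about 0.9 to 2.8 points for a period-adjusted estimate in switchers. It is near zero with equal, like-for-like switching.

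Two stronger readings are tempting and unsupported. One is that the cross-over result is bound to be seriously wrong: that would need a known period trend, known switching rates, or opposite reasons for switching in the two arms, and no section gives any of these. The other is that the trial's main comparison is undermined: the two-month comparison and its 82% power do not rest on the cross-over set. The premise is secure; the magnitude is illustrative. It should be fixed.

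**What to change.** 1. Base the confirmatory drug conclusion on the randomised two-month comparison. Label component 2 supportive, and conditional on choosing to switch.
2. Replace the selection-bias sentence with one to this effect: pairing removes stable between-patient differences, but not selection into this set by first-drug response or tolerability, nor period effects.
3. Report component 2 by sequence, with the number of switchers and their reasons in each arm. Do not rely on a period term in switchers alone (step 3).
4. Alongside it, fit a repeated-measures model for DHI on all randomised patients, stayers and switchers, with visit, current drug and pre-randomisation DHI. State its assumption that switching depends on observed DHI or on factors unrelated to later DHI. The covariance and post-switch terms are for the trial statistician to choose.

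In simulations with unstructured covariance and an assumed pattern of staggered switching, such a model was within 0.2 points, with type I error of 4–7%. It is not immune. Early intolerance correlated 0.3 with later DHI moved it by up to 0.7 points. A 25% carry-over of a 10-point difference understated the effect by 1.0 to 1.9 points unless the first post-switch score had its own drug-specific mean.

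The cost is a little more analysis and a weaker claim for component 2. No new visits are needed, because section 3b already collects DHI from stayers to month four. Reasons for switching must be recorded if they are not already.

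Sections 1a, 2a, 3b and 8k differ on time on each drug and length of participation. That is a separate inconsistency, and those passages must be reconciled.

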*** Devices ***

5. Devices

a) Please list in the space below all investigational devices to be used on subjects during this study.

b) Please list in the space below all FDA approved devices to be used on subjects during this study.

*** Drugs, Reagents, Chemicals, or Biologic Products ***

6. Drugs, Reagents, Chemicals, Biologic Products, or Dietary Supplements, Vitamins, and Other Food Agents

Pilot
Phase III

Phase I
Phase IV

Phase II
 Not Phased

List placebo if it is considered a drug (contains more than inactive ingredients). For example, normal saline is considered a drug that should be listed, whereas placebo tablets are usually inert ingredients that do not need to be listed.

b) Please list in the space below all investigational drugs, reagents or chemicals to be administered to subjects during this study. Attach all applicable Investigator Brochures in section #16 (Attachments).

c) Please list in the space below all FDA approved drugs, reagents, chemicals to be administered to subjects during this study. Attach all applicable package inserts in section #16 (Attachments).

FDA Approved Drugs, Reagents, Chemicals, Biologic Product

Drug Name	Manufacturer	Source (e.g., Pharmacy, Sponsor, etc.)	Dosage
topiramate	Janssen Pharmaceuticals, Inc	Pharmacy	25-100 mg per day
Nortriptyline	Teva Pharmaceuticals USA Inc	pharmacy	25 - 75 mg in escalating dose to self titrate

Protocol Title: A Prospective randomized cross-over trial of nortriptyline and topiramate in the initial treatment of vestibular migraine

d) Please list in the space below all dietary supplements, vitamins, minerals, or foods to be administered to subjects during this study.

Please read the IND Statements.

*** Other Levels Of Review ***

7. Other Levels Of Review

1. University Radiation Safety

Protocols that involve non-standard of care radioactive materials (which includes the terms "radioisotopes", "radionuclides", "radiopharmaceuticals", and "nuclear medicine studies", e.g., "PET", "MUGA", "Zevalin", and/or specific radionuclides such as "F-18", "Tc-99m", "Th-201", "I-131", "Ra-223", "Y-90", etc.) will receive review by the Radiation Safety Officer (RSO) and/or Radiation Safety Committee (RSC). For information on how to submit for radiation safety review, see RSC instructions or contact the Radiation Safety Officer at [name].

Not Applicable

Yes, study involves radioactive materials (per instructions, submit to RSC before IRB)

2. Institutional Biosafety

Experiments involving the deliberate transfer of Recombinant or Synthetic Nucleic Acid Molecules (e.g., Gene Transfer), or DNA or RNA derived from Recombinant or Synthetic Nucleic Acid Molecules, or Microorganisms containing Recombinant or Synthetic Nucleic Acid Molecules and/or infectious agents (including select agents and toxins as defined by CDC and/or Animal and Plant Health Inspection Service (APHIS)) into one or more human research participants must be reviewed by the SLU Biological Safety Officer. Most of these protocols also require review and approval by the SLU Institutional Biosafety Committee (IBC). Please contact the SLU Biological Safety Officer at [name] for more information.

Not Applicable

Yes, study requires Institutional Biosafety review

3. Pharmacy, Therapeutics, Nutrition, and Transfusion (PTNT) Committee

Saint Louis University Hospital requires that all research involving the administration of medications within the hospital (including outpatient areas such as the Emergency Department, Outpatient Center, Saint Louis University Hospital-South Campus, etc.) be reviewed and approved by the Pharmacy, Therapeutics, Nutrition, and Transfusion (PTNT) Committee and that study drugs are received, stored, prepared, and dispensed by the Hospital's Department of Pharmacy Services. Please contact the

Protocol Title: A Prospective randomized cross-over trial of nortriptyline and topiramate in the initial treatment of vestibular migraine

Investigational Drug Services Clinical Pharmacist at [name] or [contact] for more information.

Not Applicable
Yes, study requires PTNT review

4. Saint Louis University Hospital

All research involving Saint Louis University Hospital, including the Emergency Department, inpatient or outpatient services (including outpatient surgery at ABI and the infusion center at DOB) and medical record access, requires approval from the Saint Louis University Hospital Research Review Committee prior to study initiation. This process is designed to facilitate compliance with state and federal regulations as they pertain to research in hospitals and clinical research billing. Documents should be submitted as soon as possible, or at the latest, concurrently with IRB submission. Please contact the Research Compliance Office at [name] or [contact] of the SLU Clinical Trials Office (CTO) at [name] or [contact] for more information.

Not Applicable
Yes, study requires Saint Louis University Hospital review

5. SSMSL

All research involving SSMSL locations (including Cardinal Glennon), including inpatient or outpatient services and medical record access, requires approval from the SSM STL or SSM Cardinal Glennon Research Business Review (RBR) prior to study initiation. This process is designed to facilitate compliance with state and federal regulations as they pertain to research in hospitals and clinical research billing. While researchers can begin to complete the SSM RBR form at any time, the form should not be submitted until the IRB and the CTO have approved the study. Please contact the SSMSL Office at [name] or [contact] for more information.

Not Applicable
Yes, study requires RBR review

6. Does this project require registration on ClinicalTrials.gov, and/or is this project subject to the NIH GCP Training Requirement? (Select "Yes" if either apply)

Registration may be required if any of the following apply: 1) The project meets the FDAAA definition of an "Applicable Clinical Trial", which requires registration on ClinicalTrials.gov. 2) As of January 1, 2017, a new NIH policy mandated biomedical and behavioral "Clinical Trials" to be registered on ClinicalTrials.gov. In addition, NIH policies require personnel on NIH "Clinical Trials" to take GCP training every three years. 3) Registering may be required for Journal Publication (ICMJE). Please review relevant definitions here. Contact the CTO at [contact] with questions about registering on ClinicalTrials.gov and refer to the training page of the IRB website for information on NIH GCP Training requirements.

Protocol Title: A Prospective randomized cross-over trial of nortriptyline and topiramate in the initial treatment of vestibular migraine

*** Subject Population ***

8. Subject Population - In the space below, please detail the participants that you are requesting to recruit (include description of each group requested)

a) **Expected age range of subjects. (For example ≥ 18 yrs to 90 yrs).**

18-70 years of age inclusive

b) **Number of evaluable subjects to be accrued at SLU or SLU site (this includes all sites under the direction of the SLU PI).** 100

Exceeding the number listed here is a protocol violation. Prior IRB approval is required if additional participants are to be accrued. If applicable, this number should be consistent with your power analysis described in 3d.

c) **Number of evaluable subjects to be accrued study wide. *?HELP?***

100

d) **If including vulnerable populations (minors, pregnant women and fetuses, neonates, non-English speaking, economically or educationally disadvantaged, prisoners, adults temporarily or permanently unable to consent for themselves): 1) provide the rationale for the importance of including this population in the research, and 2) specify the measures being taken to minimize risks to potentially vulnerable subjects. Click on hyperlinks to access SLU Guidelines containing additional considerations and strategies for mitigating risks.**

n/a

e) **If women, minorities, or minors are not included, a clear compelling rationale must be provided unless not applicable. Examples for not including minors: disease does not occur in children; drug or device would interfere with normal growth and development; etc. If federally funded reference appropriate section of the sponsors protocol/grant. *?HELP?***

minors are not included in this protocol because patients will be recruited from an adult clinic and the problem is not common in children

f) **If any specifically targeted subjects are students, employees, or laboratory personnel, specify the measures being taken to minimize the risks and the chance of harm to these potentially vulnerable subjects. See SLU Guidelines for additional considerations and strategies for mitigating risks.**

g) **Describe (labeled a-c): a) who you are recruiting for this study (e.g., your patients/students/colleagues, those in existing database or registry, the general public), and b) how you are recruiting (flyers, advertisements, direct call/mailing, membership networks, in-person recruitment in clinic, classroom, public locations, etc.). For secondary data analysis or specimen studies, state how you have access to materials. Importantly: do not contact participants prior to obtaining IRB approval for your study.**

c) **Also indicate whether or not you plan to obtain personal/private information or biospecimens for the purpose of screening, recruiting, or determining eligibility of prospective subjects prior to obtaining informed consent and how (obtained by communicating with prospective subjects or obtained by accessing records**

Protocol Title: A Prospective randomized cross-over trial of nortriptyline and topiramate in the initial treatment of vestibular migraine

or stored biospecimens). Note: if you are accessing medical records other than those of your own patients or those in your immediate department, you will need to submit a HIPAA Preparatory to Research form and submit to the SLU Privacy Officer PRIOR to accessing records.

Please refer to the https://www.slu.edu/research/faculty-resources/research-integrity-safety/institutional-review-board-irb/irb_assets/guidelines_subject_recruitment.doc target=_blank>SLU IRB Recruitment Guidelines when designing recruitment strategies and upload recruitment materials to the Attachments page for IRB review. You are expected to obtain permission for individuals/organizations that assist with recruitment, and whenever possible, those assisting should share your materials with potential participants on your behalf rather than providing you with private contact information.

Patients will be selected from the busy clinical practices of Drs. [name] and other research team members. Combined, they currently see approximately five new patients with vestibular migraine per week. In addition, print advertisements in a local newspaper will be used to advertise the study. The study coordinator [name] will screen by phone patients responding to the advertisements.

* * * Subject Population * * *

8. Subject Population (continued)

Page numbers from a sponsor's protocol/grant may be referenced in 8h.

h) Inclusion and Exclusion Criteria.

Identify inclusion criteria.

Men and women aged 18 to 70 with untreated vestibular migraine variant as diagnosed by history.

Identify exclusion criteria.

Patients with allergies to nortriptyline or topiramate and their analogs or medication interactions that preclude their use. Patients under the care of a psychiatrist. Patients who are pregnant or trying to become pregnant. Patients taking more than 5 prescription medications. Patients with cancer. Patient has a history of immunodeficiency. Patient has a history of substance abuse within the preceding 6 months prior to screening. Patient has used an investigational drug or device in the the 3 months prior to screening. Patient is using marijuana for medical or other uses. Patient has any other clinically significant illness or medical condition that, in the investigator's opinion, would prohibit the subject from participating in the study. Patient with traumatic brain injury.

Due to known drug interactions, patients taking the following medications will be excluded. Nortriptyline: monoamine oxidase inhibitors (MAO) such as phenelzine. Patients on oral contraceptives will be asked to use a secondary method as nortriptyline can reduce the effectiveness of oral contraceptives.

Topiramate: acetazolamide (kidney stones), digoxin

Exclude subjects with liver dysfunction, kidney dysfunction and glaucoma (per the risks associated with topiramate).

i) Compensation. Explain the amount and schedule of compensation, if any, that will be paid for participation in the study. Include provisions for prorating payment.

Protocol Title: A Prospective randomized cross-over trial of nortriptyline and topiramate in the initial treatment of vestibular migraine

\$60 will be paid to each patient per visit that they participate in the research study. Checks will be sent monthly after each visit. Costs of the medication is standard of care. The subject will be responsible for picking up and paying for the medication at their preferred pharmacy.

j) Describe who will cover study related costs. Explain any costs that will be charged to the subject.

Association for Migraine Disorders has funded the study and will cover all costs.

k) Estimate the probable duration of the entire study including data analysis and publication. This estimate should include the total time each subject is to be involved and the duration the data about the subject is to be collected. If the study is Investigator-initiated, a timeline for individual subject recruitment, follow-up, total time for subject accrual, and data analysis for the study is required.

Patients are expected to participate for a maximum of 5 months, the study will be active with recruitment and follow-up to meet enrollment criteria for approximately 2 years.

